## 2.5 *Explanation for Choice of Comparator Intervention*

Not applicable, study without PDT is currently ongoing (study acronym DESCAY, ethical number 2018-00783) at the Orthopedic University Hospital Balgrist. The results of this prospective study will be used as reference for this pilot study results.

## 2.6 Risk / Benefits

In the following, we describe benefits, weakness, opportunities, and risks of this study.

**Benefits**

- Important topic in our society of more elderly patients with the increasing need of orthopedic implants
- Photodynamic treatment is a promising method for improving skin anti-sepsis..
- established network with infectious diseases specialists (Lead), microbiologists, dermatologists, and orthopedic surgeons

**Weakness****Opportunities**

- Improved skin antisepsis by photodynamic treatment would change routine praxis in orthopedic surgery as well as overall in surgery with the consequent reduction in morbidity, mortality, and health-care costs

**Risks**

- Minimal risk (transient erythema and pain) using PDT (no long-term sequelae)

Possible side effects of the PDT treatment are pain during PDT in the area of treatment, erythema and edema during and after light treatment (Borgia, Giuffrida et al. 2018). These side effects are self-limiting.

Since our study interventions (see above) have minimal risks for participants, it is reasonable to conduct this pilotstudy before starting a larger clinical trial with patients undergoing hip arthroplasty surgery.

## 2.7 Study Population

Twenty healthy male and female volunteers'  $\geq 18$  years will be recruited for this clinical study. The study will be approved by the local ethical committee and conducted with a study nurse ([name]) and a doctoral thesis student ([name]) in collaboration with the Clinic for Dermatology at the University Hospital Zurich, with the Institute of Medical Microbiology at the University of Zurich, and with the Orthopedic University Hospital Balgrist in Zurich. An informed consent will be obtained from each participant. We will exclude pregnant and lactating women, participants taking antibiotics in the 14 days prior to the photodynamic treatment or until follow-up at 21 days, participants who received oral retinoid therapy within the last 6 months, participants who received anti-inflammatory agents within the 14 days prior and after the photodynamic treatment, participants taking any photosensitizing drugs within 4 weeks prior to the photodynamic treatment, participants who had a history of photosensitivity disorder or having a fitzpatrick's skin phototype V-V (16)

We will not include vulnerable participants

### 3 STUDY OBJECTIVES

#### 3.1 Overall Objective

The overarching aim of this research project is to prevent orthopedic implant-associated infections. The specific aim is to evaluate the effect of photodynamic treatment on colonizing bacteria immediately before surgical skin antisepsis (aim 1) and 3 weeks later (aim 2). In addition in aim 3, we will evaluate phylogenetic similarity of same bacterial species before and after photodynamic treatment if they persist.

#### 3.2 Primary Objective

Here we use skin swabs from the groin before and after Photodynamic treatment. For all these swabs, we will use the scratching method using a scalpel as already applied in a previous study (ethical approval BASEC-Nr 2016-01017). The skin swabs will be sent to the microbiology laboratory of the University of Zurich for bacterial analysis.

We distinguish between an immediate (day 0) and long-term effect (3 weeks) investigating the skin microbiome after PDT.

In Detail:

1. Immediate effect of photodynamic treatment in combination with surgical antisepsis on bacterial skin colonization
  - 1.1. To quantitatively evaluate bacterial density and species before photodynamic treatment and after photodynamic treatment and antisepsis skin preparation
    - 1.1.1. **Parameter:** growth of bacteria (yes/no), number and identification of bacteria (species name), semiquantitative amount of bacteria
2. Long-term effect on bacterial skin colonization in the groin after photodynamic treatment
  - 2.1. To quantitatively evaluate bacterial density and species before and after 7 and 21 days of photodynamic treatment
    - 2.1.1. **Parameter:** growth of bacteria (yes/no), number and identification of bacteria (species name), semiquantitative amount of bacteria
  - 2.2. To evaluate changes of sebaceous and sweat glands after photodynamic treatment on skin biopsies
  - 2.3. **Parameters:** Number and size of glands

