## 4 STUDY OUTCOMES

### 4.1 Primary Outcome

**Outcome 1:** Immediate effect (Same day) of photodynamic treatment in combination with surgical antisepsis on bacterial skin colonization

- Skin swabs:
  - o Bacterial growth, density, and species before and immediately after PTD with standard bacterial cultures, MALDI-TOF for bacterial identification, semiquantitative amount of bacteria with dilution bacterial plates, molecular analysis using e.g RNA seq, whole genome sequencing
- Skin biopsies
  - o Changes of sebaceous and sweat glands after PDT (Histopathology with immunostaining)

**Outcome 2.** Long-term effect (1 and 3 weeks after PDT treatment) on bacterial skin colonization in the groin after photodynamic treatment

- Skin swabs:
  - o Bacterial growth, density, and species before and immediately after PTD with standard bacterial cultures, MALDI-TOF for bacterial identification, semiquantitative amount of bacteria with dilution bacterial plates, molecular analysis using e.g RNA seq, whole genome sequencing
- Skin biopsies
  - o Changes of sebaceous and sweat glands after PDT (Histopathology with immunostaining)

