## 10.3 Planned Analyses

- As a pilot study, we plan to do descriptive statistics only.
- Categorical date will be tested for differences using Fisher's exact or chi-squared tests.
- Continuous variables will be tested using Wilcoxon rank sum tests.
- Data will be analyzed using Stata® version 14.2 (Stata Corporation, College Station, TX). Two-tailed P-values <0.05 are considered statistically significant.

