### 10.3.2 Primary Analysis

Descriptive comparisons of microbiological data before and after PDT by [name], [name], and [name].

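### Some 9 to 13 results share primary status without ranking, and Section 10.3 both disclaims testing and sets a P<0.05 rule with no multiplicity control

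*Combined protocol and SAP*

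**What the plan says.** The synopsis and Sections 3.2 and 4.1 set two primary outcomes, one immediate and one long-term.

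- **Immediate swabs (3.2):** "To quantitatively evaluate bacterial density and species before photodynamic treatment and after photodynamic treatment and antisepsis skin preparation".
- **Long-term swabs (3.2):** "To quantitatively evaluate bacterial density and species before and after 7 and 21 days of photodynamic treatment".
- **Parameters for both:** "growth of bacteria (yes/no), number and identification of bacteria (species name), semiquantitative amount of bacteria".
- **Biopsies (3.2):** "Number and size of glands".
- **Molecular work (4.1, under both outcomes):** "molecular analysis using e.g RNA seq, whole genome sequencing".

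None of these sections puts one variable or one time first. The study plan table in Section 8.1 differs from them. It labels the day-0 scraping after antisepsis as the primary outcome measure, one biopsy row as secondary, and the day-7 and day-21 row of scrapings and biopsies as both primary and secondary. Section 2.4 ties the decision on a larger study to sterile cultures after PDT plus antisepsis.

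On analysis, Section 10.3 opens with "As a pilot study, we plan to do descriptive statistics only". It then names Fisher's exact, chi-squared and Wilcoxon rank sum tests and ends with "Two-tailed P-values <0.05 are considered statistically significant". Section 10.3.2 gives the primary analysis as "Descriptive comparisons of microbiological data before and after PDT", without naming a variable, a time or a test.

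**The concern.** Sections 2.1 and 5.1 make a trial in hip arthroplasty patients depend on promising results from this pilot, without saying which result or how large. With many results of equal standing, the report can lead with whichever looks best. If the P<0.05 rule is used, chance alone can supply that result. If the analysis is purely descriptive, the choice among results is still open after the data are seen. The open-ended molecular wording in Section 4.1 also allows primary measures to be added late.

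**Working it through.** **No figure to reproduce.** The plan gives 20 volunteers (Section 10.2) with no effect size, rate or power, and no familywise error rate. Its only error-rate figure is 0.05 per test.

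**Step 1: count the primary results.**
- Swabs: 3 parameters (growth; number and identity of species; amount) × 3 times (days 0, 7, 21) = 9.
- Glands: 2 parameters (number, size) × 2 biopsy times on treated skin (day 0 or 7, and day 21; Section 5.2) = 4.
- Total: 13. Counting glands once gives 9 + 2 = 11. Treating biopsies as secondary, as one row of Section 8.1 does, gives 9.

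This takes one post-baseline scraping per time point. Sections 8.3.2 to 8.3.4 list two per visit; the extra ones are not counted. Molecular read-outs are not counted either.

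**Step 2: upper figure.** Assume every result is tested at 0.05, all nulls are true and the tests are independent. The chance of at least one false positive is 1 − 0.95^m:
- m = 9: 1 − 0.630 = 37.0%
- m = 11: 1 − 0.569 = 43.1%
- m = 13: 1 − 0.513 = 48.7%

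**Step 3: allow for correlation.** The parameters come from the same people and often the same scraping, so independence is not realistic. The documents give no correlations. These figures assume equally correlated normal test statistics (200,000 simulated draws):

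| Assumed correlation | 9 results | 13 results |
|---|---|---|
| 0.3 | 33% | 42% |
| 0.5 | 27% | 33% |
| 0.7 | 20% | 24% |

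**Step 4: allow for conservative tests.** The true size of two-sided Fisher's exact at 10 v 10 is at most 1.28%. If every test were that conservative and independent, 1 − (1 − 0.0128)^m gives 11% for m = 9 and 15% for m = 13. This is an illustration only, since 10 v 10 does not describe the biopsies (5 participants) or the before/after swabs. The rank sum test applied to before/after data from the same people is also conservative: its simulated size is about 2% at a within-person correlation of 0.3 and 0.9% at 0.5.

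**Step 5: which nulls are clean.** On day 0, povidone-iodine/alcohol is applied between the two scrapings that Section 3.2 compares. A fall is then expected without any PDT effect, so for those three results the difficulty is confounding with antisepsis, not chance. Leaving them out gives 6 to 10 results: 1 − 0.95^6 = 26.5% and 1 − 0.95^10 = 40.1%, again as upper figures.

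**Step 6: what a two-group primary comparison could show.** Summing the binomial probabilities of all 10 v 10 tables with two-sided Fisher P<0.05, at assumed growth rates of 70% and 30%, gives power of about 24%.

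**The case against.** The strongest reply is that the plan disclaims inference. The synopsis, the first bullet of Section 10.3 and Section 10.3.2 all say descriptive, and no section assigns a test to a particular primary measure. A reader might infer that the plan commits to judging every result at P<0.05; the text does not go that far. What stands is a contradiction, because the same list names tests and a significance threshold, and the synopsis and the opening of Section 10 repeat the tests.

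A reader might also infer that a false positive is likely, or that 13 is a minimum. Neither is supported. Even the independent-test figure for 13 results is just under one half, and a culture without growth fixes species number and amount as well, so the measures are strongly linked. Section 8.1 supports a count of 9.

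It can also be said that the sponsor has in effect named the main result. Section 2.4 and the primary row of Section 8.1 both point to the day-0 culture after antisepsis. That is right, and it supplies the remedy, but Sections 3.2, 4.1 and 10.3.2 do not match it. Similarly, the parameter lists in 3.2 contain no molecular measure and Sections 8.2.1 and 8.2.2 assign whole-genome sequencing to the secondary outcome. Section 4.1 is therefore inconsistent on sequencing, and RNA sequencing is the part left open.

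Finally, a between-group reading shrinks the problem. The text of Section 5.2 gives controls swabs only around antisepsis, with no stated day-7 or day-21 control swabs (the flow chart is not shown). Three swab tests give at most 1 − 0.95^3 = 14%, and seven with the gland results 1 − 0.95^7 = 30%. But the primary analysis in Section 10.3.2 is before versus after, so this reading is not the plan's own.

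**Conclusion.** The point holds in this form: the primary outcome is an unranked set of roughly 9 to 13 results, and Section 10.3 contradicts itself on whether they are tested, with no multiplicity rule if they are. The false-positive risk is up to about 37% to 49%. It is about 27% to 33% at an assumed correlation of 0.5, and lower where exact or unpaired tests are conservative. These figures assume that all results are tested before versus after with no true effect; Step 5 shows that the day-0 contrast does not meet that condition. The documents do not support saying that a false positive is more likely than not. Selection among results remains open even if no P-value is reported.

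**What to change.** 1. In Sections 3.2, 4.1 and 10.3.2, name one primary result: any bacterial growth (yes/no) on the day-0 scraping after antisepsis, in line with Sections 2.4 and 8.1. Report it with an estimate and 95% CI.
2. Reconcile the control group first. Section 5.2 describes 10 participants swabbed before and after antisepsis without PDT; Section 7.1.1 gives PDT to 20, and Section 7.1.2 states that there is no control intervention. Once group sizes and the existence of a control group are settled, compare PDT plus antisepsis with antisepsis alone. Otherwise report the proportion with growth in the PDT group and its CI.
3. Label amount, species, days 7 and 21, glands and molecular work exploratory, with estimates and CIs and no significance statements. Move the open-ended molecular methods out of the primary outcome, and bring the row labels in Section 8.1 into line.
4. In Section 10.3, remove the conflict between description only and the P<0.05 rule.

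**Cost.** No extra participants, samples or visits. Other measures can no longer be called primary or significant. Section 1.15 treats changes to endpoints or the form of analysis as substantial, so ethics committee approval is needed. A 10 v 10 comparison would be imprecise (about 24% power in the example above) and should be read as an estimate, not a test.

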#### 3.3 Secondary Objectives

To evaluate phylogenetic similarity of the microbiota on the dermis before and one and three weeks following photodynamic treatment

#### 3.4 Safety Objectives

Evaluation of adverse events

## 4 STUDY OUTCOMES

### 4.1 Primary Outcome

**Outcome 1:** Immediate effect (Same day) of photodynamic treatment in combination with surgical antisepsis on bacterial skin colonization

- Skin swabs:
  - o Bacterial growth, density, and species before and immediately after PTD with standard bacterial cultures, MALDI-TOF for bacterial identification, semiquantitative amount of bacteria with dilution bacterial plates, molecular analysis using e.g RNA seq, whole genome sequencing
- Skin biopsies
  - o Changes of sebaceous and sweat glands after PDT (Histopathology with immunostaining)

**Outcome 2.** Long-term effect (1 and 3 weeks after PDT treatment) on bacterial skin colonization in the groin after photodynamic treatment

- Skin swabs:
  - o Bacterial growth, density, and species before and immediately after PTD with standard bacterial cultures, MALDI-TOF for bacterial identification, semiquantitative amount of bacteria with dilution bacterial plates, molecular analysis using e.g RNA seq, whole genome sequencing
- Skin biopsies
  - o Changes of sebaceous and sweat glands after PDT (Histopathology with immunostaining)

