### 5.2 Study Duration and Study Schedule

The expected duration of participant's participation is 35 days from first study visit to the last follow-up time to report side effects of photodynamic treatment. The screening visit can be any time before but at least 1 week before the first study visit. The study schedule is indicated below.

**Figure 1.** Flow chart

**Fig.1.** Study design of the PDT versus the control group

\* Only performed in 8 out of 10; \*\* only performed in 4 participants

At the day of inclusion, the voluntary participant will be informed and asked for signing the informed consent by [name] when fulfilling in- and exclusion criteria. This visit and the last visit (day 35 of the study) will be at the outpatient clinic for Infectious Diseases at the University Hospital Zurich. Demographic data (age, sex, current medications, and underlying diseases) will be noted.

Appointments for the photodynamic treatment (day 0) and the control visits (day 7 and 21) at the Department of Dermatology with Dr. [name] or at the Infectious Diseases department will be made

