## **8 STUDY PROCEDURES**

### **8.1 Study Flow Chart/Table of Study Procedures and Assessments**

Flow-chart see chapter 5.2.

[figure not shown]
**Study plan:** Effects of photodynamic therapy on the human inguinal skin microbiome to improve antiseptic effect

Study tasks	Screening	Intervention Period			Follow-up
		1	2	3	
Visits					
	at least -7	0	7±3	21±7	35±7
7. Participant information and informed consent	√				
8. Inclusion- and exclusion criteria	√				
9. Demographic data	√				
10. Inguinal skin scraping before photodynamic treatment		√			
11. Natural bacterial porphyrin fluorescence photography		√	√	√	√
12. Study intervention: Photosensititer application, followed by fluorescence photography Photodynamic therapy (PHT) (1x) over 15 minutes at the dermatology ward		√			
13. Primary outcome measure: Skin antisepsis in the groin, skin scraping after antisepsis		√			
14. Secondary outcome measure: Punch biopsy  specimen of the MAL-PDT area (immediately after PDT) and of an untreated area as a control		√		√	
15. Primary and secondary outcome measure: Inguinal skin scraping and punch biopsy  of the MAL-PDT area			√	√	
16. (serious) adverse events			√	√	√
17. End of study information of study results					√

 optional, only in 5 volunteers

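### Gland change is ranked as a primary outcome but comes from an optional 5-volunteer biopsy substudy, and the only continuous-data test named is unpaired although the biopsies are paired

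*Combined protocol and SAP*

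**What the plan says.** **Rank of the outcome.** Section 4.1 lists "Changes of sebaceous and sweat glands after PDT (Histopathology with immunostaining" twice, once under the same-day Outcome 1 and once under the long-term Outcome 2. Section 3.2 has "To evaluate changes of sebaceous and sweat glands after photodynamic treatment on skin biopsies" as item 2.2 of the primary objective, under the long-term effect only, with number and size of glands as the parameters. The synopsis does the same. Section 8.2.1 puts histopathology under assessment of the primary outcome. Section 4.2 lists only phylogeny as secondary.

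The 8.1 table differs. Row 14, the punch biopsy of treated and untreated skin, is headed "Secondary outcome measure". Row 15, scraping together with punch biopsy, carries a label that covers both ranks. The table's footnote calls the biopsy "optional, only in 5 volunteers".

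**What is sampled.** Sections 5.2 and 8.3.1 describe a substudy of 5 volunteers with three biopsies each: treated right groin on day 0 or day 7, untreated left groin on day 0 or day 7, and treated area on day 21. Section 8.2.1 asks for a separate consent. No biopsy before treatment is scheduled.

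**Analysis.** Section 10.3 opens with "As a pilot study, we plan to do descriptive statistics only". It then says "Continuous variables will be tested using Wilcoxon rank sum tests" and "Two-tailed P-values <0.05 are considered statistically significant". It names no paired test and gives the biopsies no analysis of their own. Section 10.3.2 describes the primary analysis for microbiological data only.

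**The concern.** A primary outcome should be one that the trial collects in its analysis population and has a stated way to analyse. Gland change is collected in at most a quarter of the planned 20 volunteers (5/20), by option, and the protocol disagrees with itself on whether it is primary. The plan's general rule for continuous variables would send gland size to a test for two independent groups, although each treated biopsy has its comparator in the same person.

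Gland destruction is one of the two mechanisms in the hypothesis (10.1), and the pilot is meant to inform a trial in hip arthroplasty patients (2.1, 5.1). If the general rule is applied, the trial could report a primary result on glands with a P-value that does not fit the data. If the analyst switches to an exact paired test, no pattern in 5 pairs can meet the plan's threshold. Without a decision in advance, the choice of test after seeing five results would decide the wording of a primary conclusion.

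**Working it through.** The plan gives no calculation for the biopsy substudy, and 10.2 gives only the total of 20 without effect size, spread or power. There is therefore no stated figure to reproduce. The check is of what each test can return with the planned number.

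**Inputs.** n = 5 volunteers with biopsies (5.2, 7.1.1, 8.1); treated and untreated skin from the same person (5.2); two-tailed 0.05 and the rank sum test (10.3).

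**1. The named test, unpaired rank sum, 5 treated against 5 untreated.** The most extreme result is complete separation of the two sets. Smallest exact two-sided P = 2/C(10,5) = 2/252 = 0.008. This is below 0.05, but it counts 10 biopsies from 5 people as 10 independent observations.

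**2. A test that respects the pairing, signed-rank or sign test.** The most extreme result is all 5 volunteers changing in the same direction. Smallest exact two-sided P = 2/2^5 = 2/32 = 0.0625, above 0.05. Six pairs would be the first number able to pass: 2/2^6 = 2/64 = 0.031.

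**3. Sensitivity to how the paired P is computed.** For 5 pairs all in one direction, the signed-rank sum is 15, its null mean 7.5 and its null variance 5 × 6 × 11/24 = 13.75.
- Normal approximation without correction: z = 7.5/√13.75 = 2.02, P = 0.043.
- With continuity correction: z = 7.0/√13.75 = 1.89, P = 0.059.
- Exact: P = 0.0625.

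So the same five results fall on either side of 0.05 according to the approximation.

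**4. Loss of one volunteer.** Section 10.3.1 analyses only those who complete the study, and 10.4 imputes nothing. With 4 pairs the exact paired minimum is 2/2^4 = 2/16 = 0.125, and the unpaired minimum is 2/C(8,4) = 2/70 = 0.029.

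**5. Same-day pairs.** Under 5.2 and 8.3.1 the first treated-side biopsy may be immediate or on day 7. If k of the 5 are taken on day 0, the same-day gland component of Outcome 1 has at most k pairs, and k is not fixed. Section 7.2.1 (step 5) and row 14 of the 8.1 table show this biopsy on the treatment day, so those places need reconciling with 5.2.

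**6. What a descriptive summary can say.** If all 5 volunteers show smaller glands on the treated side, the exact (Clopper–Pearson) 95% lower limit for the proportion is 0.025^(1/5) = 0.478. The interval is 48% to 100%.

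**The case against.** The strongest reply is that 10.3 and the synopsis both announce a descriptive analysis, and that no test is specifically assigned to gland data. On that reading no P-value would be produced, and the limits in steps 1 and 2 would not matter. This has force: a descriptive report is one legitimate outcome of the plan as written. But the lines that follow in 10.3 name tests and a significance threshold for all categorical and continuous variables, and nothing exempts the biopsies. The conflict over rank and the 5-of-20 coverage remain under either reading.

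It is also fair to say that the biopsies are already called a substudy in several places, and that row 14 of the 8.1 table stands against most of the document, with row 15 mixed. That makes the inconsistency easy to repair. It does not remove it.

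Four stronger readings are tempting and not supported:
- That the planned test cannot reach P<0.05. The named test can; the bar at 0.0625 belongs to an exact paired test, which the plan does not name.
- That no paired rank test could pass at 5 pairs. The uncorrected normal approximation gives 0.043, and the plan does not say how P-values for rank tests are computed.
- That only 4 volunteers have biopsies. A footnote to Figure 1 says "only performed in 4 participants", but the figure cannot be seen here, so what it marks is unknown. The text uses 5 throughout.
- That the unpaired test must exaggerate the effect. The direction of its error depends on the within-person correlation, which the documents do not give; with positive correlation it would usually err towards a larger P. What can be said is that its P-value does not have its nominal meaning for these data.

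**Conclusion.** The point holds as an inconsistency of outcome rank combined with an analysis rule that does not fit the paired biopsies. Gland change is primary in the synopsis, 3.2, 4.1 and 8.2.1, secondary or mixed in 8.1, and optional in 5 volunteers. The one continuous-data test named ignores the pairing (minimum P 0.008), and the exact two-sided test that respects it cannot fall below 0.0625. This rests on 5 complete pairs, on the untreated left groin being the comparator, and on 10.3 applying to gland data because nothing excludes it.

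Five consistent within-person comparisons would still be useful descriptive evidence on mechanism. They cannot carry a primary, significance-tested claim. The point does not touch the validity of the bacterial outcomes. It should be corrected, and wording is enough.

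**What to change.** - **Synopsis, 3.2, 4.1, 8.1 and 8.2.1:** give gland number and size one rank throughout, as a descriptive outcome of the biopsy substudy, and align the labels in rows 14 and 15 of the 8.1 table.
- **4.1, Outcome 1:** remove gland change from the same-day outcome, or limit it there to volunteers biopsied on day 0 and report how many that is. Reconcile the biopsy timing in 5.2 and 8.3.1 with 7.2.1 and 8.1.
- **10.3:** exempt the biopsies from the rank sum test and from the 0.05 threshold. State that each volunteer's treated and untreated values will be listed with the paired differences, and that the number changing in each direction will be given with an exact confidence interval and no P-value.
- **5.2:** say what the Figure 1 footnote giving 4 refers to, if the figure itself does not make it clear.

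The cost is protocol wording, with no change to biopsies or visits. The downside is that the trial no longer claims a primary result on glands.
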